## Data Analysis Plan

## Statistical considerations

**General Statistical Approach:** Patients will be randomized in a 1:1 manner to Coq10 or placebo; randomization will be stratified by study center and gender. This study includes a comprehensive survey of patient status using a broad set of clinical assessments and laboratory assays designed to assess the response to treatment Unless otherwise specified, two-sided P < 0.05 will be considered statistically significant. Statistical analyses will be carried out using SAS Version 9.4 or higher.

**a) Baseline:** Differences in continuous baseline variables will be compared by a two-sample t test. The Mann-Whitney U test will be used in the case of non-normal distribution. For baseline categorical variables, Fisher's exact test will be used.

**b)** Evaluating the efficacy of CoQ10 in GWI: The primary analysis is to compare treatment groups on change from baseline SF-36 physical function score over time (6 monthly time points from Week 4 to Week 24) in a repeated measures setting using a final two-sided 0.049 level of significance (a 0.049 level is being used at the end of the study instead of 0.05 to account for the interim analysis further described below). This will be carried out using a mixed model (MM) analysis of variance (ANOVA) with effects for treatment, time, baseline physical function score and the randomization strata of study center and gender. The within-patient correlation structure will be assumed to be unstructured. If this analysis shows a significant treatment difference across time or a significant treatment-by-time interaction, comparisons across treatment (significance level at each time point using a Bonferroni alpha-adjustment (significance level at each time point = 0.049 divided by 6, the number of planned post-baseline time points) to account for the multiple comparisons. Data will be analyzed as an intention-to-treat model; i.e., all

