randomized subjects will be included using available data (i.e., a patient does not have to provide data through the end of the study to be included in the analysis; this is the strength of the MM ANOVA approach). A secondary supportive analyses will be carried out where missing physical function data at each time point are first imputed via monotone multiple linear regression imputation, under the assumption the missing data mechanism is missing at random prior to carrying out the mixed model analysis. The imputation regression model at each time point will include randomized treatment, measures of the primary outcome at earlier time points and baseline covariates that will be specified in the final detailed statistical plan. Fifty imputed datasets will be created, and the MM ANOVA will be run on each data set; the 50 MM ANOVA results will then be combined across the data sets using PROC MIANALYZE in SAS to obtain one overall assessment of treatment difference on the imputed data.

**c) Sample size justification and power analysis:** In this study population, we rely on the literature of Phase III studies of other inflammatory states to determine assumptions required for sample size calculations. Our primary clinical outcome variable is physical function of the SF36 measured over time (approximately monthly from week 4 through week 24; i.e., 6 measurements over time). Our current data suggests a coefficient of variation (CV) of approximately 0.40 for physical function at a given time point. Assuming this and assuming a relative increase in SF36 of at least 21% for Coq10 over placebo at each time point, then there is a 0.525 treatment effect size at each time point. Under this effect size, power is at least 95% to detect a treatment difference over time using an evaluable group sample size of n=90 subjects at a two-sided 0.049 level of significance regardless of the within- patient correlation between time points. To account for approximately 10% attrition, 100 subjects per group will be randomized. Such an evaluable sample size will also allow at least 80% power to detect a relative increase t of 21% separately at each time point after using a Bonferroni multiple comparison adjustment across the six time points.

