**d)** Subgroup analysis on the primary endpoint: Treatments will be compared within each gender. The purpose of this analysis is not to show a statistically significant Coq10 effect on the primary endpoint within each gender (due to potential lack of power; e.g., if there are 25 evaluable women in each treatment group, power ranges from approximately 50% to 95% depending on the within-patient correlation between time points under the effect size assumptions used in the primary power calculation), but rather to investigate consistency of treatment difference across genders. In addition, treatment-by-gender interaction will be assessed in a mixed model repeated measures model that includes the main effects in the primary analysis and a term for treatment-by-gender interaction; an interaction p-value <0.15 will be considered as possibility indicating lack of consistency in treatment effect across gender. Similar analyses will be conducted to assess consistency of results across study centers.

e)Other clinical efficacy end points will look at each of the self-report assessment measures across the domains of fatigue, pain, sleep, and the SF36 subscales of function and severity. Objective measures include laboratory data that could reasonably be considered a surrogate for illness severity (e.g., measures of immune activation, inflammation, cell function, and NPY), a focus of several of our prior publications ([name] 2002, 2009, 2010; Maher 2007; Broderick 2009, 2010). Other objective measures include cognitive assessments and the activity monitor data which will be measured at each assessment point at the beginning of the study and on the 24th week of treatment. These will all be analyzed in a similar manner as the primary endpoint. We will also look at the effect of duration of study drug exposure on a case by case basis if there are individuals who fail to complete 24 weeks of study drug, and will also look at the change in CoQ10 levels as a predictor of response. These endpoints are considered exploratory and no adjustment of significance level for the multiple comparisons will be applied.

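### The primary model as listed gives one baseline slope to all six visits and omits treatment-by-time; if baseline correlation fades, the per-visit comparisons, week 24 most of all, are noisier than they need be

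*Combined protocol and SAP*

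**What the plan says.** All of this is in the Data Analysis Plan, under Statistical considerations.

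- Section b) compares the arms on "change from baseline SF-36 physical function score over time (6 monthly time points from Week 4 to Week 24". The model has "effects for treatment, time, baseline physical function score and the randomization strata of study center and gender". On the covariance it says: "The within-patient correlation structure will be assumed to be unstructured".
- The primary test is made "using a final two-sided 0.049 level of significance". If it shows "a significant treatment difference across time or a significant treatment-by-time interaction", the arms are compared at each visit, with "significance level at each time point = 0.049 divided by 6".
- No baseline-by-time term appears anywhere. Treatment-by-time is tested but is not among the listed effects.
- Section c) sizes the trial from a "coefficient of variation (CV) of approximately 0.40 for physical function at a given time point". It takes no credit for baseline adjustment and gives no correlation between baseline and any visit.
- Section e) says of the other efficacy endpoints: "These will all be analyzed in a similar manner as the primary endpoint". It calls them exploratory.

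**The concern.** The covariance between visits is left free, but the relation of baseline to outcome is held equal at every visit. If baseline predicts week 4 better than week 24, the fitted common slope is set mainly by the early visits and over-corrects the late ones. The mismatch goes into the residual variance of the visit-specific treatment comparisons.

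What is at stake is precision at single visits. This matters somewhat because section c) promises at least 80% power at each visit after the Bonferroni adjustment, and that promise has little margin before baseline adjustment is counted. The incomplete effects list adds a practical problem: a programmer who follows it literally cannot produce the interaction test or the per-visit comparisons that the plan goes on to require.

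**Working it through.** **Inputs from section c).** Effect size 0.21/0.40 = 0.525 at each visit; 90 evaluable per arm; two-sided 0.049 overall and 0.049/6 = 0.00817 per visit. The correlations below are assumptions.

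**The plan's own power figures.** Power = Φ(0.525·√(90/2)/√v − z), where v is the residual variance relative to the raw variance, and 0.525·√45 = 3.522.
- Per visit, v = 1, z = 2.645: Φ(0.877) = 81.0% (80.0% by noncentral t). The plan says at least 80%.
- Overall, worst case of visit correlation 1, z = 1.969: Φ(1.553) = 94.0%. With v = (1+5r)/6 it is 95.6% at r = 0.9 and 98.2% at r = 0.7. The plan says at least 95%, so this agrees closely.

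**Cost of one slope, with treatment-by-time in the model.** Scale baseline and every visit to unit variance. Let b_j be the true slope at visit j (equal to its correlation with baseline), and S the residual covariance with elements s_jk and s_jj = 1 − b_j². In large samples with complete data:
- the common slope tends to b* = (1'S⁻¹b)/(1'S⁻¹1);
- the variance at visit j is proportional to s_jj + (b_j − b*)²;
- the variance of the equal-weight average (weights c = 1/6) is proportional to c'Sc + (mean b − b*)².

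Separate slopes remove the squared terms.

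**Worked example.** Let correlation depend only on the gap between visits, falling linearly so that baseline correlates 0.80 with week 4 and 0.50 with week 24. Then mean b = 0.650 and b* = 0.730.
- Week 24: (0.75 + (0.50 − 0.730)²)/0.75 = 0.803/0.75 = 1.070.
- Average: (0.344 + (0.650 − 0.730)²)/0.344 = 0.3506/0.344 = 1.019.

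**Range.** Ratios are common-slope variance over separate-slope variance. Power is for week 24 at 0.049/6.

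| Assumed baseline correlation, week 4 to week 24 | Average | Week 24 | Power, common to separate slopes |
|---|---|---|---|
| Constant 0.5, 0.7 or 0.8 | 1.000 | 1.000 | unchanged |
| Moderate fading, about 0.62-0.81 to 0.27-0.60 | 1.002-1.025 | 1.01-1.08 | see next row |
| Example above, 0.80 to 0.50 | 1.019 | 1.070 | 90.1% to 92.2% |
| Autoregressive, lag-one 0.90 (0.90 to 0.53) | 1.072 | 1.148 | 89.2% to 93.5% |
| Autoregressive, lag-one 0.80 (0.80 to 0.26) | 1.070 | 1.176 | 76.4% to 84.2% |

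Over lag-one values of 0.80 to 0.95, the ratios run from 1.05 to 1.08 for the average and 1.09 to 1.18 at week 24. At lag-one 0.80 the common slope leaves a week-24 residual variance of 0.931 + 0.164 = 1.095, which is worse than no baseline adjustment (1.00). Overall power exceeds 99.6% under either model in every row.

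These ranges describe the patterns tried and are not bounds. If baseline fades from 0.80 to 0.50 while all post-baseline visits stay equally correlated at 0.75, the ratios are 1.13 and 1.18. In an artificial extreme (0.80 to 0.40, with 0.80 between visits) b* is 1.364, beyond every true slope, and both ratios exceed 2. The conclusion does not rest on that case.

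**Literal list, treatment main effect only.** The treatment estimate then weights the visits by the same S⁻¹1 that defines b*, so the weighted mismatch Σw_j(b_j − b*) is zero. The ratio is exactly 1.000 in every pattern.

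**Cost of the extra slopes.** Simulating 1,500 trials of 90 per arm with constant correlation 0.7 gave a ratio of 1.0005, so no measurable loss. The 0.80-to-0.50 example gave 1.023 for the average and 1.068 at week 24, in line with the formula.

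**The case against.** The best case against the point has four parts.

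1. The effects list is evidently a summary: it also omits treatment-by-time, which the plan then tests. The absence of baseline-by-time is therefore weak evidence that it was ruled out. This stands as a caution. It is also a reason to complete the list, because a literal reading gives one slope.
2. A reader might infer that the primary contrast loses precision as a matter of course. The documents do not support that. The loss needs baseline correlation that fades, which they neither state nor exclude, and it needs treatment-by-time in the model with an equal-weight average over visits. Under the literal list it is zero.
3. Week 24 is not the primary contrast. It is one of six comparisons, made only after a significant overall or interaction result, and under moderate fading its power stays above the promised 80% with either model. This stands. Only the steep end of the range, lag-one 0.80, falls below 80%.
4. The section e) endpoints are exploratory, and many have fewer visits. Table 1 shows cognitive testing at three post-baseline visits, while section e) describes the activity and cognitive data as taken at the start and at week 24. The six-visit figures do not carry over to them, and with a single post-baseline visit the issue does not arise.

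None of this shows a cost to adding the term. A common slope is a valid prespecified choice, but separate slopes lose nothing measurable when the correlation is constant and gain when it fades.

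**Conclusion.** The point holds as a minor and conditional gain in precision. As written, section b) gives baseline one slope for six visits and lists an incomplete set of effects. If baseline correlation fades, week-24 variance is about 1-8% higher than it need be under moderate fading, and up to about 18% under steep autoregressive decay. The six-visit average loses about 0-3%, or up to about 8% under steep decay. With constant correlation the loss is zero, and with only a treatment main effect the loss in the treatment effect is zero.

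A reader might go further and infer bias or an underpowered primary test. Neither follows. Under randomization the single slope does not bias the treatment contrast. The overall power claim comes from the unadjusted CV and does not depend on the slope.

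All sizes rest on assumed correlations, unit-scaled variances and a large-sample, complete-data calculation that simulation supports.

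**What to change.** In section b), name treatment-by-time and baseline-by-time (a separate baseline slope at each post-baseline visit) among the primary model effects. State that the primary treatment difference is the equal-weight average over the six visits, if that is what is meant. In section e), use the same two terms for endpoints with more than one post-baseline visit.

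The cost is one line of text and about five degrees of freedom for the baseline slopes (six slopes in place of one), with about 180 to 200 subjects in the model. No additional data are needed. The change should be made before unblinding.

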
Laboratory Variables	Screening on-site	T0 on-site	4 wk on-line	8 wk on-site	12 wk on-line	16 wk on-site	20 wk on-line	24 wk on-site	28 wk on- line
CBC with diff		Ø		Ø		$\odot$		Ø	
CMP	Ø	Ø	1			Ø		Ø	
U/A	Ø	Ø				Ø		Ø	
Cortisol series		Ø		Ø		Ø		Ø	
Autonomic measures		Ø				Ø		Ø	
HPG axis		Ø				Ø		Ø	
HPT axis		Ø				Ø		Ø	
CoQ10		Ø		Ø		Ø		Ø	
Exclusion HIV, Hep B, C, RA, CBC, RF, LFTS, CRP, HbA1c	Ø								
Stored sample for biomarker studies	Ø	Ø		Ø		Ø		Ø	

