Informed consent will be obtained by the study investigator or by an IRB-approved delegate after a screening interview, but prior to the initiation of any study procedures. Subjects will be given a local telephone number and will have an opportunity to ask questions about the procedures. They will be informed that their decision to or not to participate will have no bearing on their medical care and that, if they choose to participate, they may withdraw at any time without loss of VA benefits to which they are entitled. There is no coercion; potential subjects are given the opportunity to ask questions, take home materials that accurately reflect the study protocol, and volunteer or not without impacting their relationship with providers. For the virtual platform, Miami VA research staff will mail 2 copies of the informed consent to the prospective participant. Once the signed copy is received, the Miami VA research staff will contact the participant to initiate study procedures. A consent form will be mailed to a potential participant only if he/she is interested in the study. If the individual does not return a signed consent form to the Coordinator, the individual will demonstrate that he/she has opted to not participate in the study. Subjects are compensated for their travel and effort in small part.

After a screening visit, they are compensated \$125 for assessment at Baseline and 3 follow-up visits that involve relatively lengthy self-report instruments, a physical exam, a cognitive assessment fitting, given an activity meter with instructions and a blood draw. This initial visit requires 3-4 hours to complete. They return for additional visits that focus on cognitive testing and a brief physical exam at month 2, 4, and 6. For the virtual platform, Miami VA research staff will ask the participant to complete the cognitive testing online at baseline, 2, 4, and 6. At these visits, the Miami VA Nurse Coordinator will ask the same health status and medication questions via telephone, in place of the physical exam procedures. At the 6-month visit, the Nurse Coordinator will complete the end of study procedures and ask the participant to return any unused medications to the Miami VA via mail.

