## Screening labs

Screening labs as outlined will be shipped to the Miami lab. This will include a history and physical exam; blood tests directed at detecting conditions, which would explain the severity of the illness and thus be exclusionary (e.g. untreated hypothyroidism, severe liver disease, anemia etc.). Additional blood tests that are being evaluated to better understand the illness or develop the data needed to prove their utility as surrogates for severity of illness. Blood volume at any one visit will not exceed 120 ml (8 tablespoons). Risk of blood draw includes local bruising and vasovagal responses to phlebotomy (fainting). In the on-site initiation visit as well as the week 8,16, and 24 week visits, the subject will have a brief physical exam emphasizing vital signs, autonomic function (lying and 10 minute stand BP and P), and trigger point assessment. For the virtual platform, the subject will not have this brief physical exam.

For the virtual platform, the Miami VA research team will ship collection boxes directly to the participant. Laboratory tests will be combined for the screening and baseline visits. During the screening visit, (after signed consent is received), the tests will include all baseline tests and the exclusion tests. Samples will be drawn and packed by phlebotomists at Quest Laboratories in the participant's local area and shipped via overnight express to Miami VA.

The subject will be given a web link to the REDCap platform of self-administered questionnaires to be completed within 48 hours prior to the drug initiation visit. Scoring will follow standardized scales.

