During the screening visit, the subject will be taught the proper technique for using the activity monitor, assign and practice the web login for the REDCap based platform by performing the core assessments on the computer in the office, assisted by research staff as needed, and perform the studies that require a face-to-face interaction (SCID). The SCID will be performed by telephone for the virtual platform. They also complete the following standardized scales either at home on a weblink within 4 days of each scheduled assessment or on site (cognitive testing is always on site). All subjects wear an activity monitor from the first assessment throughout the 6-month period, which links in any wireless environment to update the activity / sleep data files. For the virtual platform, all assessments will be completed via the telephone interview format or via online surveys in the REDCap platform. The research staff will mail the Fitbit directly to the subject's home, after the screening interview and satisfactory completion of the laboratory tests and assessment forms that confirm eligibility.

**Medication review:** review for exclusionary meds, document all medications and over the counter supplements.

**Screening blood draw:** TSH, ANA, RF, CMP, CBC, ESR, HIV serology, Hep and Hep C, CRP, Hemoglobin A1c for screening purposes. Females will also have a pregnancy test. The focus is on exclusionary conditions. A sample also will be drawn for the biorepository.

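### The SF-36 is scheduled twice before study drug, but the primary model adjusts for one baseline score, so precision that costs nothing to obtain goes unused

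*Combined protocol and SAP*

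**What the plan says.** Section b) of the Data Analysis Plan compares the arms on "change from baseline SF-36 physical function score over time (6 monthly time points from Week 4 to Week 24" and lists the model terms as "effects for treatment, time, baseline physical function score and the randomization strata of study center and gender". There is one baseline term.

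The laboratory part of Table 1 heads its first two columns "Screening on-site T0 on-site". The self-report part has nine columns in the same on-site and on-line order, and the SF-36 is marked in all nine. The first mark looks deliberate, because the two Hamilton scales are left blank in the screening column.

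The text under Screening labs describes both administrations. At the screening visit participants "practice the web login for the REDCap based platform by performing the core assessments on the computer in the office". They later receive a link to "self-administered questionnaires to be completed within 48 hours prior to the drug initiation visit".

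Baseline is not formally defined, but Recruitment Process and Informed Consent places payment "for assessment at Baseline and 3 follow-up visits" after the screening visit. For the virtual platform, Screening labs states: "Laboratory tests will be combined for the screening and baseline visits". It does not say whether the SF-36 is also combined.

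**The concern.** A single SF-36 physical function score mixes a participant's usual level with measurement error and short-term fluctuation. A second reading taken before treatment helps to separate the two, so adjusting for both usually explains more of the post-baseline variation than adjusting for one. The plan schedules that second reading and gives it no use in the analysis.

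What is at stake is the width of the confidence interval for the primary effect. This would matter most if the true effect is smaller than planned. That is possible, because section c) takes its assumptions from other inflammatory conditions, and in the pilot the combined-sex sample showed no significant benefit on self-rated health. The entry criteria set no SF-36 threshold, so selection on the screening score is not an evident reason to leave it out.

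**Working it through.** **Inputs from section c).** Effect size 0.21/0.40 = 0.525; 90 evaluable per arm; two-sided alpha 0.049; six post-baseline visits. The correlation and the screening-to-T0 gap are not given and are assumed below.

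**The plan's own figure.** With no baseline adjustment, the variance of the six-visit mean, in units of the single-visit variance, is (1+5ρ)/6. The worst case is ρ = 1. Power = Φ(0.525·√(90/2) − 1.969) = Φ(3.522 − 1.969) = 94.0%. It is 95.6% at ρ = 0.90 and 97.1% at ρ = 0.80. The plan states at least 95%, so its figure reproduces to within about a point.

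**Equal correlation ρ between all visits.** T0 is both subtracted and adjusted for, so the treatment contrast is the same as for raw scores.
- One covariate: V1 = (1+5ρ)/6 − ρ²
- Both covariates: V2 = (1+5ρ)/6 − 2ρ²/(1+ρ)

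| ρ | V1 | V2 | Variance reduction |
|---|---|---|---|
| 0.4 | 0.340 | 0.271 | 20% |
| 0.5 | 0.333 | 0.250 | 25% |
| 0.6 | 0.307 | 0.217 | 29% |
| 0.7 | 0.260 | 0.174 | 33% |
| 0.8 | 0.193 | 0.122 | 37% |

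At half the planned effect (0.2625), power rises from 86.0% to 94.0% at ρ = 0.5 and from 93.1% to 98.8% at ρ = 0.7. At the planned effect it exceeds 99.9% either way.

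**Exponentially decaying correlation, r·φ^lag** (lag in months, screening 0.5 or 1 month before T0). The variance with both scores is v − c′S⁻¹c. Here v is the variance of the six-visit mean, c its covariances with the two pre-treatment scores, and S the covariance matrix of those two scores. The last column uses the mean of the two scores as the only pre-treatment term. Each range covers the two gaps.

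| r, φ | Both scores: variance vs T0 alone | Mean: variance vs T0 alone |
|---|---|---|
| 0.7, 0.95 | 14.8% to 16.2% lower | 14.4% to 16.1% lower |
| 0.8, 0.90 | 5.7% to 7.1% lower | 4.2% to 6.7% lower |
| 0.8, 0.80 | 1.6% to 2.4% lower | 1.7% lower to 0.4% higher |
| 0.9, 0.80 | 0.6% to 1.0% lower | 0.3% to 2.6% higher |

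Over r = 0.7 to 0.9 and φ = 0.80 to 0.95, entering both gives 0.6% to 16%. With r = 1, meaning no measurement error, the gain is zero.

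**Stable trait plus decay plus noise.** The correlation is T + A·φ^lag with T + A + noise = 1. With T = 0.3 to 0.6, noise 0.1 to 0.3 and φ = 0.5 to 0.9, entering both lowers the variance by about 3% to 28%.

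**Some participants with one reading.** If a share s has T0 only, 1/V = (1−s)/V2 + s/V1. At equal correlation 0.7 the standard-error ratio against T0 alone is 0.817 for s = 0, 0.853 for s = 25% and 0.895 for s = 50%.

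**The case against.** One baseline covariate in a repeated-measures model is standard and valid, and the trial does not depend on a second one for its stated power. That stands in full. A reader might infer that the primary analysis is wrong or the trial underpowered, but the reproduced power figure does not support this.

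A reader might also infer that the undefined baseline lets two rival primary results be drawn from the same data. The documents do not support that strength of claim, because they name baseline as a visit separate from screening, and T0 is the natural reading. What is missing is a one-line definition.

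The equal-correlation range is a tempting headline. It treats the months from screening to week 24 like the gap from screening to T0, whereas section b) specifies an unstructured correlation. It is best taken as the favourable end.

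The two readings may also differ in quality. The screening one is a login practice in the office with staff help available, and the T0 one is self-administered by web link. If the screening reading is noisier, the gain falls. Finally, the documents do not confirm two SF-36 readings for virtual-platform participants. These points reduce the expected gain and rule out simple averaging, but they do not argue against entering both scores.

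**Conclusion.** The point holds as a low-cost improvement. Two SF-36 scores are scheduled before study drug, and the primary model uses one. Neither score can be affected by treatment, so adjusting for both does not bias the comparison. The benefit may be negligible or substantial, depending on how quickly scores drift and how much of their variation is noise, and the documents settle neither. The calculations assume complete data and equal variance at each visit. The gain is nil only if the score has no measurement error and each reading depends on the past only through the one before it, which is unlikely for a self-report scale.

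**What to change.** In section b) of the Data Analysis Plan:

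- Define baseline as the T0 SF-36 physical function score for the change from baseline.
- Enter the T0 and screening physical function scores as two separate covariates. Do not use their mean, which can be less precise than T0 alone when correlation decays quickly.
- Name the same two covariates in the imputation model, whose baseline covariates are at present left to the final detailed statistical plan.
- If the screening score is missing, impute it from baseline data only, so that every randomized subject stays in the analysis.
- State whether virtual-platform participants complete the SF-36 at both screening and T0.

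The cost is a few lines of text and one more model parameter with 200 subjects. The change adds no assessment to the schedule and should be fixed before unblinding.

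### Holm's step-down would declare at least as many visits as the planned single-step Bonferroni, at the same 0.049 family-wise limit: a minor but free improvement

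*Combined protocol and SAP*

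**What the plan says.** The primary analysis in section b) of the Data Analysis Plan is a mixed model for change in SF-36 physical function over "6 monthly time points from Week 4 to Week 24", "using a final two-sided 0.049 level of significance". The model includes the baseline score, study center and gender. The visit comparisons are conditional: "If this analysis shows a significant treatment difference across time or a significant treatment-by-time interaction", the arms are compared at each visit with a "Bonferroni alpha-adjustment (significance level at each time point = 0.049 divided by 6, the number of planned post-baseline time points".

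Section c) supplies the planning figures: a "coefficient of variation (CV) of approximately 0.40 for physical function at a given time point", "assuming a relative increase in SF36 of at least 21% for Coq10 over placebo at each time point", and hence "there is a 0.525 treatment effect size at each time point". With 90 evaluable subjects per group, it says the design "will also allow at least 80% power to detect a relative increase t of 21% separately at each time point" after the Bonferroni adjustment.

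The plan mentions no step-down procedure, gives no reason for the single-step version, and asks for no simultaneous confidence intervals that would need it.

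**The concern.** The visit comparisons are the only formal means in section b) of saying at which visits CoQ10 differs from placebo, including week 24, and section c) makes a power claim for them. Single-step Bonferroni holds all six comparisons to the threshold that strict error control requires only of the smallest p-value. Holm's procedure uses the same six p-values, gives the same 0.049 guarantee and can only add declared visits. What is at stake is how completely the visit pattern is reported. The trial's answer on efficacy is not at stake.

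**Working it through.** **Inputs from the plan.** Family-wise level 0.049 two-sided, six visits, the baseline score in the model, and the conditional opening test (section b). CV 0.40, relative increase 21%, 90 evaluable per group (section c).

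**Assumed, because the documents give no value.** Exchangeable correlation ρ among baseline and the six visits, taken as 0.5, 0.7 and 0.9.

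**1. The plan's own figures.**
- Effect size: 0.21/0.40 = 0.525.
- Per-visit level: 0.049/6 = 0.00817, critical z = 2.645.
- Noncentrality without baseline adjustment: 0.525 × √(90/2) = 3.522.
- Power: Φ(3.522 − 2.645) = 81.0%, or 80.0% by the noncentral t with 178 df.

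The stated figure of at least 80% reproduces.

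**2. Why Holm dominates.** Order the six p-values and compare them in turn with 0.049/6 = 0.00817, 0.049/5 = 0.0098, 0.049/4 = 0.01225, 0.049/3 = 0.0163, 0.049/2 = 0.0245 and 0.049, stopping at the first failure. The first threshold is Bonferroni's and each later one is larger, so every visit declared by Bonferroni is declared by Holm. Family-wise error is at most 0.049 under any correlation, so the unstructured covariance is no obstacle. Requiring a positive opening test can only lower that error. None of this depends on simulation.

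**3. Bonferroni power in the planned model.** Adjusting for baseline multiplies the residual SD by √(1 − ρ²).
- ρ = 0.5: 0.525/√0.75 = 0.606; 0.606 × √45 = 4.067; Φ(4.067 − 2.645) = 92% (91.6% by t).
- ρ = 0.7: 0.525/√0.51 = 0.735; 0.735 × √45 = 4.932; Φ(4.932 − 2.645) = 98.9% (98.7% by t).
- ρ = 0.9: 0.525/√0.19 = 1.204; 1.204 × √45 = 8.080; power is effectively 100%.

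**4. Size of the gain.** This was simulated with 200,000 trials per scenario: six correlated normal statistics, 90 complete subjects per arm, baseline-adjusted, and the opening test (overall or interaction) applied at 0.049. The residual between-visit correlation is ρ/(1 + ρ). The effect is the same at all six visits.

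| True effect | ρ | Week 24, Bonferroni | Week 24, Holm | Other measure, Bonferroni to Holm |
|---|---|---|---|---|
| 0.525 | 0.5 | 92% | 97% | all six declared: 69% to 90% |
| 0.525 | 0.7 | 98.9% | 99.8% | mean visits declared: 5.93 to 5.99 |
| 0.525 | 0.9 | about 100% | about 100% | no change |
| 0.40 | 0.5 | 68% | 79% | – |
| 0.40 | 0.7 | 87% | 94% | all six declared: 57% to 83% |

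**5. Effect at only three of the six visits (0.525, adjusted).** At ρ = 0.5, true visits declared rise from 2.77 to 2.82 of 3. At ρ = 0.7 they rise from 2.97 to 2.98. Realised family-wise error rises from about 2.3% to about 4.4%, below 4.9%. If the effect is present at the first three visits and then stops (ρ = 0.7), the chance of falsely declaring week 24 goes from 0.8% to 1.7%.

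**The case against.** The strongest case for leaving the plan alone is that Bonferroni is valid, pre-specified and matched to the power statement, and that it already finds nearly everything if the planning assumptions hold. At effect 0.525 and correlation 0.7 it declares 5.93 of 6 visits on average. The gain is largest when the effect is equal at all visits, where there is no timing to discover, and small when timing does vary. Holm spends more of the permitted error when only some visits have an effect, makes each visit's threshold depend on the other p-values, and has no simple matching simultaneous intervals.

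All of that stands as a limit on the size of the point. None of it is a reason to prefer single-step Bonferroni: the extra realised error stays within the limit the plan chose, and the plan calls for no simultaneous intervals.

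A reader might infer three stronger things that the documents do not support.
- **That the stated 80% leaves no margin.** The 80.0% is for an unadjusted t-test. The planned model includes baseline, and under the assumed correlations Bonferroni power is then 92% or more at effect 0.525, so the stated figure is conservative.
- **That Bonferroni under-spends alpha across correlated visits and Holm recovers it.** If no visit has an effect, Holm's first step is the same 0.049/6, so its family-wise error is identical. Holm makes no use of the correlation either.
- **That the efficacy conclusion is at risk.** The visit comparisons only follow a positive opening test and cannot alter it.

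**Conclusion.** The point holds as a minor, free improvement and not as a defect. That Holm never declares fewer visits, at the same 0.049 limit, is a mathematical fact and needs no assumption. The size of the gain does rest on assumptions: exchangeable correlation of 0.5 to 0.9, 90 complete subjects per arm and, for the larger gains, an equal effect at every visit. It runs from nothing, at correlation 0.9, to 5 percentage points of week-24 power (92% to 97%, correlation 0.5) at the planned effect. At a true effect of 0.40, which is not the plan's figure, it is 11 points (68% to 79%) at correlation 0.5 and 7 points (87% to 94%) at 0.7. Free here means no cost in guaranteed error or sample size; realised error can rise within the limit. The change affects only which visits are declared significant.

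**What to change.** In section b), before unblinding, replace the Bonferroni rule with Holm's procedure: order the six visit p-values, compare them with 0.049/6, 0.049/5, 0.049/4, 0.049/3, 0.049/2 and 0.049, and stop at the first failure. Leave the opening test, the primary test and the 0.049 level as they are. In section c), keep the statement of at least 80% and label it as the conservative, Bonferroni-level per-visit figure.

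The cost is one sentence in section b) and a label in section c), with no extra subjects, data or alpha. The final detailed statistical plan that the document anticipates is a natural place for it. If simultaneous intervals are wanted, they can still be shown at the Bonferroni level. The change must be made before unblinding, because a switch to Holm after the visit results are known would not be credible.
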